APPENDIX L: CASE REPORT FORMS112
APPENDIX M: INVESTIGATIONAL PLAN REVISIONS.....113

LIST OF TABLES

Table 1. Follow-up Windows	26
Table 2. Data Collection Summary.....	27
Table 3. Unavoidable Events	38
Table 4. Heart Mate II Study Rates	44
Table 5. Study Oversight Contact Information.....	60
Table 6. Investigator Reporting Responsibility	68
Table 7. Sponsor Reporting Responsibility	70

TABLE OF FIGURES

Figure 1. Study Design Flowchart	17
Figure 2 Annual Survival versus Hospitalization versus NYHA	58

Trial Contact Information

Sponsor, Manufacturer & Distributor	Sunshine Heart, Inc. [name] Tele: [name] [contact] www.sunshineheart.com
-------------------------------------	---

Clinical/Technical Support [contact]-SHCPULSE)

INTRODUCTION

PURPOSE

Sunshine Heart is sponsoring a prospective, multi-center, randomized trial to assess the safety and efficacy of the C-Pulse® System (“C-Pulse”).

The purpose of the study is to determine whether the use of the C-Pulse as a treatment for patients in moderate to severe heart failure (HF) has demonstrated safety and efficacy, such that the C-Pulse System merits Food and Drug Administration (FDA) approval to market the device in the United States.

STUDY SIZE AND DURATION

This clinical study is anticipated to commence October 2012. The enrollment and 12 month follow-up duration of the study is expected to be 3.5 years. The primary study population will include 388 subjects enrolled and randomized in up to 40 centers in the United States (US) and potentially additional sites in Canada. The treatment group will include 194 subjects randomized to and implanted with C-Pulse® System and the control group will include 194 subjects randomized to and followed according to the same follow-up schedule as the treated subjects. All patients must be consented prior to performing any study related procedures. A patient is considered enrolled upon signing the informed consent. To minimize the burden to the patient, data collected as standard of care and not for the specific reason for study eligibility may be used for baseline data points as outlined in the informed consent. These tests will suffice for the baseline dataset if collected within the specified baseline data collection timeframe prior to implant. The subjects will be assigned a screening number upon signing the consent.

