All subjects who do not meet the eligibility requirements will be promptly study exited. Study exit of these screen failure subjects must be documented. Only the subjects who meet the eligibility criteria will proceed to randomization. The subjects will be assigned a randomization number. The period of subject follow-up will be a minimum of 12 months to assess the safety and efficacy. Post 12 months, subjects will continue to be followed at 18 months and then annually during long-term follow-up to five years.

The study will be conducted in accordance with Code of Federal Regulations (CFR) Parts 11, 50, 54, 56 and 812. A progress report of the clinical outcomes will be given to the Data and Safety Monitoring Board (DSMB) following enrollment of the first forty (40) randomized patients and at least twice annually based on study progress. The recommendation(s) from the DSMB may be circulated to each of the Investigation Review Boards (IRB) and Ethic Committees (if applicable) participating in the study upon request.

BACKGROUND

Heart Failure (HF) represents a major and growing public health concern in terms of incidence, prevalence, morbidity, mortality and economic cost. Chronic HF is predominantly the result of ischemic heart disease or idiopathic dilated cardiomyopathy.

Chronic HF is conventionally treated with drugs. However there are many circumstances where drug therapy is insufficient or where the heart has become refractory to drug therapy. Cardiac Resynchronization Therapy (CRT) is indicated in patients with HF who have ventricular dyssynchrony, commonly evidenced by a widened QRS complex. Resynchronization therapy is suitable for approximately 30% of moderate HF patients, and has been shown to provide significant clinical improvement [as measured by NYHA Class, quality of life (QOL) score, 6 minute walk test, freedom from advanced heart failure treatments, etc]¹. As many as 30% of patients who have CRT implants do not have a satisfactory response (“non-responders”). Further, many patients initially have a good response but then develop more advanced symptoms.

Heart transplantation is an effective therapy for end stage NYHA Class IV patients. The number of donor hearts falls short of meeting the needs of patients and many patients are excluded because of age (the upper limit for transplant being approximately 65 years)².

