Report all associated adverse events. Update the device tracking records with all products. If the device is not returned to Sunshine Heart Inc., justification must be provided in the log.

Subject Withdrawal and Study Exit

A Study Exit record shall be completed if subject is unable to or refuses to continue participation in the study. Notify the Sunshine Heart clinical support team as soon as possible upon learning of a subject withdrawal/study exit.

If the subject fails to comply with follow-up visits, the study center must make repeated attempts to contact the subject. Each attempt to contact the subject must be documented in the subject's records and in the database.

If the subject officially withdraws from the study, the investigator will document the reason for withdrawal and indicate any relationship of the withdrawal to the study or the device on the eCRF.

If a subject withdraws from the study at any time, there will be no penalty or loss of future medical care.

STATISTICAL METHODS AND DATA ANALYSIS

Analysis Population

All randomized subjects will be included in the evaluation of the primary efficacy objective. Subjects will not be allowed to cross-over. All subjects implanted with the C-Pulse System will be included in the evaluation of the primary safety objective. In the event a randomized subject does not receive the implant or does not receive the randomized therapy, the subject will be analyzed according to the randomized assignment for the primary analyses. Additional supporting analyses of the primary efficacy endpoint will be conducted (as treated and per-protocol) which exclude subjects who do not receive the randomized treatment or those with major protocol deviations. The defined analysis cohorts are:

- Intent to treat: All randomized subject irrespective of treatment actually received (primary efficacy analysis)
- As treated: All randomized subjects receiving treatment as randomized
- Per protocol: All randomized subjects without major protocol deviations

Primary Efficacy Endpoint

The primary efficacy endpoint is defined as freedom from worsening heart failure related hospitalization, LVAD implant, heart transplant, and death.

The primary efficacy endpoint includes all occurrences of worsening heart failure events and will be analyzed utilizing a multiple failure time analysis.

Hypotheses

H_0 : HR=1,

H_A : HR \neq 1,

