where HR is the hazard ratio; the ratio of the C-Pulse treatment group worsening heart failure event hazard relative to the Control group worsening heart failure event hazard. This is designed to demonstrate that C-Pulse[®] therapy increases the freedom from worsening heart failure events as compared to Control as evidenced by a HR that is less than 1 and the upper bound of the two-sided 95% confidence interval for the HR excludes 1. All occurrences of worsening heart failure events will be included in the primary endpoint analysis. Details of the analysis methods can be found in the Statistical Analysis Plan.

Primary Efficacy Endpoint Sample Size

Sample size was estimated using SAS v9.2 software under two sided test for a difference in freedom from worsening heart failure. For the purposes of sample size estimation, a time to first event analysis was used to provide a conservative estimate of the required number of events and subjects. The minimum required sample size and total number of worsening heart failure events was calculated under the following assumptions:

- Significance level = 0.05
- Power = 0.80
- Proportion for 6 month freedom from worsening heart failure event in Control group = 0.72
- Underlying treatment effect on the hazard ratio scale: HR = 0.70
- Accrual time of 2.5 years
- Minimum follow-up of 12 months
- 10% Attrition per year
- 1:1 allocation ratio

Under the above assumptions a total of 265 subjects with at least one worsening heart failure events are required to be observed to ensure adequate power which indicates a total of 388 subjects randomized. As the primary analysis will include all worsening heart failure events in a multiple event analysis, the power for the detection of a difference in freedom from worsening heart failure event may be greater than 80%.

Justification for Primary Efficacy Endpoint Sample Size Assumptions

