¹³ PMA P100047: FDA Summary of Safety and Effectiveness Data HeartWare® Ventricular Assist System : Left Ventricular Assist Device.

¹⁴ PMA P060040/S5: FDA Summary of Safety and Effectiveness Data Thoratec HeartMate® 11 Left Ventricular Assist System (LVAS).

- Summary of baseline demographic, medical history and heart failure related assessments
- Summary of all available follow-up assessments

The initial enrollment period for the IDE study is intended to provide a period of review for safety to ensure that the risk/benefit assessment has not worsened and that the product/procedural/training enhancements have indeed provided the potential for improvement in outcomes such as exit site infections. Specifically, if more than 8 of 20 implanted subjects experience an exit site infection per the protocol definition, within six months of device implant, the enrollment will be halted until a resolution is agreed upon with FDA, the clinical advisors and Sunshine Heart Inc. A stopping rule will also be followed in the event more than 7 of 20 implanted subjects die during device support within twelve months of device implant and the mortality event is adjudicated as possibly or definitely related to the procedure, therapy or device. The company will halt enrollment while FDA, the clinical advisors and Sunshine Heart Inc. come to a resolution on continuing the trial.

Since this interim analysis is only for the purposes of safety and there is no potential for early stopping for efficacy, there is no type I error inflation and no adjustment required to the primary analysis of the protocol.

Interim Analysis

An interim analysis will be conducted when approximately 194 randomized subjects have been followed to twelve months. The interim analysis will evaluate the primary endpoint of a comparison of worsening heart failure events using all accrued, fully adjudicated primary endpoint events of recurrent worsening heart failure. The results of the interim analysis will be evaluated by the DSMB against a futility stopping rule for a finding of efficacy on the primary objective. Details of the analysis methods can be found in the Statistical Analysis Plan.

Additionally, an assessment of early efficacy will be made. The interim analysis will have a significance cutoff for superiority. At the interim analysis, the DSMB may make one of the following recommendations:

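### On the listed inputs, 265 first events is neither the number that 80% power requires nor the number that 388 subjects would be expected to yield

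*Combined protocol and SAP*

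**What the plan says.** The section Primary Efficacy Endpoint Sample Size (under Statistical Methods and Data Analysis) sizes the trial on first events: "a time to first event analysis was used to provide a conservative estimate of the required number of events and subjects". It lists a two-sided 0.05 level, power 0.80, 72% of controls event-free at 6 months, hazard ratio 0.70, 2.5 years of accrual, 12 months' minimum follow-up, "10% Attrition per year" and 1:1 allocation. From these it states that "a total of 265 subjects with at least one worsening heart failure events are required to be observed to ensure adequate power". The same sentence then derives the number of subjects from this event count: "which indicates a total of 388 subjects randomized".

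Other sections fix the surrounding design:

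- Study Size and Duration: "The primary study population will include 388 subjects enrolled and randomized", and "The period of subject follow-up will be a minimum of 12 months to assess the safety and efficacy". It puts enrolment plus 12-month follow-up at 3.5 years, which agrees with 2.5 years of accrual plus 1 year.
- Primary Efficacy Endpoint: "The primary efficacy endpoint includes all occurrences of worsening heart failure events and will be analyzed utilizing a multiple failure time analysis".
- Interim Analysis: "An interim analysis will be conducted when approximately 194 randomized subjects have been followed to twelve months". It has a futility rule and an efficacy cutoff. The boundaries are left to the Statistical Analysis Plan, and the available text does not give them.

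**The concern.** The sentence makes two claims: that 265 first events are what 80% power requires, and that this requirement leads to 388 subjects. The first depends only on the level, power, hazard ratio and allocation. The second depends on the event rate, accrual, follow-up and attrition. Both can be checked from the listed inputs, and neither reproduces.

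This matters because 265 is the only event requirement stated for the primary endpoint in the available text, and it is worded as something that must be observed. Someone who tracks accrued first events against it would expect a trial run exactly as planned to fall about 22 short, and might wrongly conclude that the trial was short of information.

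**Working it through.** **Inputs.** All are from Primary Efficacy Endpoint Sample Size. Three assumptions are not in the text: uniform accrual, exponential event and loss times, and equal attrition in both arms.

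- Control hazard: −ln(0.72)/0.5 = 0.657 per year
- Treatment hazard: 0.70 × 0.657 = 0.460 per year
- Loss hazard η: −ln(0.9) = 0.105 per year, or 0.10 if 10% is read as a rate
- Accrual A = 2.5 years, minimum follow-up F = 1 year

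**Step 1: first events required for 80% power, fixed design.**

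- Schoenfeld: 4(1.96 + 0.8416)² / (ln 0.70)² = 246.8, so 247
- Freedman: (1.96 + 0.8416)² × (1.70/0.30)² = 252.0, so 253 after rounding up

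The stated 265 is 7% above 247 and 5% above 253. At 265 events the power would be 82.7% (Schoenfeld) or 81.9% (Freedman).

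**Step 2: first events expected from 388 subjects.** In an arm with event hazard λ, the probability of an observed first event is

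p = λ/(λ+η) × {1 − [e^(−(λ+η)F) − e^(−(λ+η)(F+A))] / [(λ+η)A]}

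| Loss assumption | p control | p treatment | Mean | Events from 388 | Subjects for 265 events |
|---|---|---|---|---|---|
| η = −ln(0.9) | 0.6822 | 0.5661 | 0.6241 | 242.2 | 265/0.6241 = 424.6 |
| η = 0.10 | 0.6852 | 0.5689 | 0.6270 | 243.3 | 265/0.6270 = 422.6 |
| none | 0.7455 | 0.6248 | 0.6851 | 265.8 | 386.8 |

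A simulation of 20,000 trials gave the same means: 242.2 events with loss and 265.8 without.

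**Step 3: which row fits the plan.** The plan's own ratio is 265/388 = 0.683. The row without attrition gives 0.685; the rows with attrition give 0.624 to 0.627. The number of subjects points the other way. A Lakatos-type log-rank calculation needs 390 to 396 subjects for 80% power with attrition and 358 to 361 without it, so 388 sits near the with-attrition figure. The two numbers in the sentence appear to rest on different attrition assumptions.

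**Step 4: first-event power at 388 with the listed attrition.**

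- Schoenfeld, Φ(√D × |ln 0.70|/2 − 1.96): 79.3% at D = 242.2 and 79.4% at 243.3
- Freedman, Φ(√D × 0.30/1.70 − 1.96): 78.4% and 78.6%
- Log-rank calculation: 79.2% to 79.8%
- Simulation: 78.7% (standard error 0.3)

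**The case against.** **The figure has little practical force.** The trial is fixed by subjects and follow-up, the interim is triggered by subjects followed, and the primary analysis uses all recurrent events. As a requirement, 265 errs on the high side. All of this stands, and it is why the point is minor.

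**The 247 to 253 is a fixed-design figure, but the plan has an interim efficacy look.** This also stands. For one look at 40% to 70% of the information, O'Brien-Fleming-type boundaries raise the requirement to at most about 257. Pocock boundaries give about 265 to 284. Since no boundary is given in the available text, an allowance that produced 265 cannot be excluded. But it is not among the listed inputs, and it would not repair the second step: with the listed attrition, 388 subjects would still be expected to give 242 to 243 events.

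**Other routes reach about 265.** With attrition kept and minimum follow-up raised to 18 months, 388 subjects give 265.0 events (loss hazard −ln 0.9). That repairs the link to 388, but it contradicts the listed 12 months and leaves 265 above the 80% requirement. Power of 82% by Freedman gives 266 events, but it contradicts the listed 0.80 and does not repair the link.

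**The expected yield rests on unstated assumptions.** Uniform accrual and constant hazards are assumed here, not given. A different accrual pattern or hazard shape would change the 242 to 243, but not the 247 to 253.

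A reader might infer from the match of 0.683 to 0.685 that attrition was certainly omitted. The documents do not support that: the SAS output is not in them, and other routes exist. A reader might also infer that the trial is too small. That is not supported either, because 388 is within about 0.4% to 2.2% of the 390 to 396 that the log-rank calculation gives.

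**Conclusion.** The mismatch is real. On the listed inputs, 265 is about 5-7% above the fixed-design requirement for 80% power and about 9% above what 388 subjects would be expected to yield. Confidence in the mismatch is high, given uniform accrual and exponential event and loss times. The cause is unproven: omitted attrition fits best, while an undisclosed interim allowance or longer follow-up remains possible.

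The consequence is minor. First-event power at 388 is about 78-80%, close to the planned 80%, and the plan notes that the recurrent-event analysis may have more. The error lies in the event count and its link to 388, not in the sample size.

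**What to change.** 1. Check 265 against the SAS output.
2. State whether it includes attrition, and whether it includes an allowance for the interim efficacy look. If it does include an interim allowance, add that to the listed inputs.
3. Rewrite the sentence so that three figures are given separately and agree: the first events required, the first events expected from 388 subjects, and the resulting first-event power. On a fixed design with the assumptions used here, these are about 247-253, about 242-243 and about 78-80%. The sentence should then present 0.80 as the target and not as exactly achieved.
4. Name the accrual pattern and the event and loss distributions used.

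The cost is one look at existing output and a change of wording in one section. The 388 subjects, the follow-up, the visits and the interim decision rules do not change.

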Prior to enrolling patients, each investigational center IRB will be required to approve the study Investigation Plan and the Patient Informed Consent. In addition, patients will be required to provide written informed consent for enrollment.

Patients will undergo a pre-implant baseline assessment to ensure they meet the inclusion and exclusion criteria prior to randomization. The baseline assessment must occur within 30 days prior to implant. Patient informed consent must be signed prior to conducting any screening or baseline testing procedure performed solely for study purposes. A screening number will be assigned upon consent. To minimize the burden to the patient, data collected as standard of care and not for the specific reason for assessing study eligibility may be used for baseline data points as outlined in the informed consent. These tests will suffice for the respective portion of the baseline dataset if collected within the pre-implant evaluation prior to randomization.

When a subject has met all Inclusion/Exclusion Criteria for the study, he/she will be randomized and assigned a randomization number by the center. The treatment subjects must proceed to implant within the window (≤ 30 days from consent to implant).

If the subject does not meet the inclusion/exclusion requirements, he/she will be study exited.

In accordance with the ethical principles that have their origin in the Declaration of Helsinki, each subject must be informed about the study and the patient or legal representative must sign and date an agreement acknowledging that participation in the study is voluntary. The Patient Informed Consent Form will be provided to the patient in the language he/she is able to read and understand. (Refer to Appendix E for the sample Consent Forms). The original signed Informed Consent will be retained in the individual Participant Study folders, and copies of the signed Informed Consent Form will be provided to the patient and to the hospital medical records of the patient.

Patients shall be consented for follow-up to five years.

Subject Withdrawal or Loss to Follow-Up

In the event a subject chooses to withdraw from the clinical study, the investigational site should attempt to ensure that any adverse events are resolved and documented as such. A Study Exit record must be completed and the subject will no longer be followed in the clinical study.

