In the event the subject becomes lost to follow-up, the investigational site should make two documented attempts to contact the subject. A Study Exit record must be completed and the subject will no longer be followed in the clinical study.

Data Collection Overview

A review of patient files is required to determine preliminary eligibility according to patient inclusion and exclusion criteria. Baseline data including functional tests must be collected no more than **30** days prior to randomization. Baseline imaging such as echo and CT scans must be collected no more than 90 days prior to randomization. See the data collection table for details.

Follow-up data will be collected at the time of implant, hospital discharge, at planned follow-ups (6 week, 3, 6, 12, 18-month and annually from the implant date thereafter up to 5 years). All serious adverse events will be collected throughout the study until closure.

All study subjects will follow the prescribed follow-up scheduled despite randomization. Day 0 for the treatment group will be the day of implant. Day 0 for the Control Group will be the day of randomization. Each group will continue with optimal medical therapy for the duration of the study, including all standard of care medications and treatments including transplant, VAD, etc. If the subjects are transplanted or placed on another device they will be censored from the primary endpoint analysis and study exited. Subjects implanted with the C-Pulse will be followed until device removal. If the PIL is explanted and not replaced, the subject will be followed for safety until removal of the entire system.

Data will be collected via electronic data capture (EDC) screens referred to as e-case report forms (eCRFs). Echocardiogram tapes and digital storage media must be documented in the patient medical record for source documentation.

Table 1, below outlines the data collection with the appropriate follow-up time windows.

Table 1. Follow-up Windows

Evaluation	Time Window
Pre-Implant Evaluation	No more than 30 days prior to implant
Randomization	Post Baseline Testing and Pre-Implant
Implant	Day 0 (Treatment Group) – Implant Day 0 (Control Group) – Randomization
Pre-Discharge	Within 36 hours prior to discharge
6 – week follow-up	Days 42 ± 7 Post-Implant
3 – month follow-up	Days 90 ± 14 Post-Implant
6 – month follow-up	Days 180 ± 30 Post-Implant
12 – month follow-up	Day 365 ± 30 Post-Implant
18 – month follow-up	Day 540 ± 30 Post-Implant

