The primary safety endpoint is 12 month freedom from serious adverse events that are adjudicated definitely related to device, therapy or procedure and resulting in either surgical intervention or death. All serious adverse events that are adjudicated by CEC to be definitely related to device, therapy or procedure and result in either surgical intervention or death will be included in the analysis. Events will be reported by number of event and proportion of subjects with event along with the ninety-five percent binomial exact confidence limits. Only first event counts towards the endpoint for each subject.

The proportion of C-Pulse[®] subjects free from serious adverse events that are adjudicated definitely related to device, therapy or procedure and result in surgical intervention or death through 12 months following implant and will be compared to the performance goal (PG) of 0.60.

The hypotheses are:

$$H_0: \Pi \leq PG,$$

$$H_A: \Pi > PG,$$

where Π is the 12 month freedom from serious adverse events that are definitely related to device, therapy or procedure and resulting in either surgical intervention or death and PG is the performance goal. If the lower, two-sided, 95% confidence bound is greater than 0.6 the objective will be met.

Primary Safety Endpoint Sample Size

Sample size was estimated for a combined freedom from serious adverse events adjudicated definitely related to device, therapy or procedure resulting in surgical intervention (to repair, replace or remove the implanted device) or death. The minimum required sample size and total number of device related deaths and device related surgical intervention events was calculated under the following assumptions:

- Significance level = 0.05
- Power = 0.80
- 12 month freedom from serious adverse events definitely related to device, therapy or procedure resulting in either surgical intervention (to repair, replace or remove implanted device) or death event of 70%.
- Minimum follow-up of 12 months

Under the above assumptions a minimum of 182 subjects are required.

Justification for Primary Safety Endpoint Sample Size

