The poolability of the primary efficacy endpoint across clinical sites will be assessed using a covariate adjusted proportional hazards regression model including an interaction term for clinical site and treatment group. In the event statistical evidence of a difference in treatment effect by site is found, an analysis utilizing a random effects model with a random effect for site will be conducted.

Type I Error Control for Secondary Objectives

The secondary efficacy objectives will be tested in a hierarchical fashion in the order listed only in the event the primary efficacy objective is met, thereby preserving an overall Type I error rate of 5%.

Handling of Missing Data

For the primary efficacy analysis, subjects lost to follow-up or explanted will be censored at the date of the last assessment.

Additional analyses of the follow-up assessments of KCCQ, six minute walk and LVEF will be conducted to assess the impact of missing data at month 12. The Wilcoxon Sign-Rank test with the worst rank imputed for data missing due to death, LVAD transplant, heart transplant or explant (in order of time to outcome) will be used to assess treatment differences in the continuous parameters while including subjects who withdrew from randomized treatment prior to the 12 month assessment. Multiple imputation analyses will be conducted to assess the robustness of the study results against data missing due to losses to follow-up and study non-compliance or un-interpretable test results.

Impact of Covariates on the Potential Treatment Differences

Additional exploratory statistical analyses of the primary and secondary study results will be conducted to assess for impact of selected baseline and follow-up parameters on the observed treatment differences. This will involve the stratification of results by categorical parameters and covariate adjusted regression analyses for the assessment of interaction with randomization assignment. Of particular interest will be an assessment for any treatment differences in the efficacy or safety parameters by gender. Other baseline covariates of interest will include classification based on race/ethnicity, age at implant, INTERMACS profile, NYHA, etiology (ischemic/non-ischemic), CRT/ICD therapy, angina, arrhythmia, hyperlipidemia and diabetes and the continuous covariates of baseline six-minute walk, KCCQ and MLWHF.

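### The primary safety test is a crude binomial proportion in all implanted subjects, with no stated rule for subjects whose follow-up ends before 12 months

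*Combined protocol and SAP*

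**What the plan says.** - **Estimate and success rule.** Primary Safety Endpoint compares the share of C-Pulse subjects free of a qualifying event through 12 months after implant with a performance goal of 0.60. On method it says: "Events will be reported by number of event and proportion of subjects with event along with the ninety-five percent binomial exact confidence limits". On success: "If the lower, two-sided, 95% confidence bound is greater than 0.6 the objective will be met".
- **Who is counted.** Analysis Population: "All subjects implanted with the C-Pulse System will be included in the evaluation of the primary safety objective".
- **How follow-up can end early.** Subject Withdrawal or Loss to Follow-Up says, for both situations: "A Study Exit record must be completed and the subject will no longer be followed in the clinical study". Data Collection Overview adds: "If the subjects are transplanted or placed on another device they will be censored from the primary endpoint analysis and study exited". It also says: "Subjects implanted with the C-Pulse will be followed until device removal". Removal of the percutaneous lead alone does not end safety follow-up.
- **Missing data.** The only censoring rule in Handling of Missing Data is for efficacy: "For the primary efficacy analysis, subjects lost to follow-up or explanted will be censored at the date of the last assessment".
- **Sizing.** Primary Safety Endpoint Sample Size gives a minimum of 182 from 0.60 against 0.70, significance level 0.05, power 0.80 and at least 12 months of follow-up. It lists no attrition. The efficacy sizing does: "10% Attrition per year".

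**The concern.** No sentence says how an implanted subject who leaves event-free at, say, two months is scored. The two nearest rules do not help. The Handling of Missing Data rule is confined to efficacy. The Data Collection Overview sentence does not say which primary endpoint it means, and a binomial proportion has no way of using a censored observation.

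Taken together, Analysis Population and Primary Safety Endpoint most naturally put every implanted subject in the denominator and every observed event in the numerator. For subjects who are lost or withdraw, unobserved time then counts as event-free, which can only raise the estimate. The opposite choice, dropping event-free leavers, biases the estimate downwards and costs power.

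One threshold decides the safety objective, and Secondary Efficacy Endpoints makes secondary testing depend on it. A scoring choice left open could be made after the data are seen.

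**Working it through.** **Inputs from the documents.** Goal 0.60, expected freedom 0.70, lower limit of a two-sided 95% interval, stated minimum 182; 194 planned for implant (Study Size and Duration).

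**Assumptions.** No exit rate is given for implanted subjects, so a = 10% in the year is borrowed from the efficacy sizing, with 5% and 20% as a range. Event timing is not given, so a fraction f = 0, 0.5 or 0.75 of the 12-month events is placed at implant and the rest at constant hazard. Exits are independent of events unless stated.

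**1. The plan's own figure.** n = [(1.96·√0.24 + 0.8416·√0.21)/0.10]² = 181.1, so 182 reproduces. It assumes complete 12-month follow-up.

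**2. Exact rule with complete follow-up.** With 194 implanted, 131 must be event-free: the exact lower limit is 0.6045 at 131 and 0.5991 at 130. P(X ≥ 131) is 1.8% at true 0.60 and 79.8% at true 0.70.

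**3. Lost or withdrawn subjects scored event-free.** Let S be true freedom, S₀ = 1 − f(1 − S), λ = −ln(S/S₀) and μ = −ln(1 − a). The observed event proportion is f(1 − S) + S₀·[λ/(λ+μ)]·(1 − e^−(λ+μ)). For S = 0.60, f = 0, a = 0.10: λ = 0.5108 and μ = 0.1054, giving (0.5108/0.6162)·(1 − 0.54) = 0.3813. Crude freedom is 0.6187 and P(X ≥ 131) = 6.0%. For f = 0.5 and 0.75, crude freedom is 0.6097 and 0.6050.

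| Chance of passing at true 0.60 | f = 0 | f = 0.5 | f = 0.75 |
|---|---|---|---|
| 5% loss/withdrawal | 3.4% | 2.6% | 2.2% |
| 10% loss/withdrawal | 6.0% | 3.5% | 2.6% |
| 20% loss/withdrawal | 15.8% | 6.3% | 3.6% |
| 10% exits, half competing | 3.4% | 2.6% | 2.2% |
| 10% exits, three-quarters competing | 2.5% | 2.2% | 2.0% |

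The nominal 2.5% is exceeded once loss and withdrawal pass 2.4, 4.7 or 9.0% in the year.

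**4. Event-free leavers dropped, observed events kept.** At S = 0.70, f = 0, a = 0.10, event-free completers are 0.70 × 0.90 = 0.63 and observed events 0.2856. The target becomes 0.63/(0.63 + 0.2856) = 0.688. Power is about 66, 61 and 58% for the three timings, and at true 0.60 the chance of passing is below 1%.

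**5. Event-free leavers scored as failures.** True 0.70 becomes 0.63, and P(X ≥ 131) = 11%.

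**6. Time-to-event estimate.** Kaplan-Meier with a log-log limit, all 10% exits being losses censored at exit (simulated, 194 implanted): 2.1% pass at 0.60 for all three timings; power at 0.70 is 78.7, 79.9 and 80.3%. Censoring at the last scheduled visit instead gives power of about 74 to 78%, because events between visits are kept while the matching event-free time is discarded.

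**7. Informative loss.** With correlation 0.3 between event and exit times (Gaussian copula), passing at true 0.60 is 3.8, 2.7 and 2.4% for Kaplan-Meier, against 8.3, 3.7 and 2.5% for the crude proportion.

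**The case against.** **A rule may exist elsewhere.** The efficacy, interim and secondary sections defer to a Statistical Analysis Plan whose text is not available here. The safety section makes no such reference, but a rule there cannot be excluded. This limits confidence.

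**The inflation rests on assumptions.** The 10% is borrowed. Procedure-related events plausibly cluster at implant, and Appendix B describes feasibility subjects going on to transplant, LVAD or recovery, so many exits may be competing. In those settings the table is near nominal. This stands. A reader might infer that the safety test is shown to be anti-conservative. The documents do not support that: the scoring is unspecified, and dropping event-free leavers errs the other way.

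**Kaplan-Meier changes the quantity.** A reader might conclude that Kaplan-Meier, with every exit censored, should replace the proportion. That goes too far. A subject with an unrelated death, LVAD or transplant and no qualifying event really is free of the endpoint as defined. Censoring such subjects estimates freedom as if those exits could not happen. If all 10% of exits are competing, Kaplan-Meier targets 0.70 when actual freedom is 1 − 0.2856 = 0.714 (constant hazard). The Data Collection Overview sentence is weak support for censoring them, since LVAD and transplant are themselves events in the primary efficacy endpoint.

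**The goal is on a crude scale.** Table 4 gives crude proportions (90/133 and 88/133). But those patients were followed regardless of transplant or explant, which this trial does not do. With complete follow-up, the estimate proposed below equals the crude proportion, so 0.60 keeps its meaning.

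**Conclusion.** The gap is real in the text available and should be fixed; confidence is medium. Under the natural reading, an inference from two sections, the error rate at 0.60 is about 6.0, 3.5 or 2.6% at 10% loss or withdrawal, against 1.8% with complete follow-up and 2.5% nominal. With mostly perioperative events or mostly competing exits it is close to nominal. At 10% exits and constant hazard, power at 0.70 runs from 90% (leavers scored free) through 66% (event-free leavers dropped) to 11% (scored as failures), so the unwritten choice can decide the result. The sizing of 182 is arithmetically correct for complete follow-up, and nothing here shows that 194 is the wrong number.

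**What to change.** - Make the primary safety estimate a 12-month time-to-event freedom in implanted subjects. Censor withdrawal and loss at the date of exit, not at the last scheduled assessment. Treat unrelated death, LVAD, transplant and any device removal that is not itself an endpoint event as competing events. The estimate is then one minus the cumulative incidence, which equals Kaplan-Meier when there are no competing exits.
- Compare its two-sided 95% log-log lower bound with 0.60.
- Report three sensitivity analyses: Kaplan-Meier with all exits censored, the planned exact binomial, and a worst-case bound counting lost or withdrawn subjects as failures. The last is a bound, not a test.
- State that 182 assumes complete 12-month follow-up.
- Separately, reconcile the two meanings of surgical intervention. The endpoint definition leaves it unrestricted, while the sizing limits it to repair, replacement or removal of the device.

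**Cost.** Analysis wording only; Kaplan-Meier curves are already planned under Additional Supportive Analyses. Limits are slightly wider, with power about 79 to 80% for 194 implanted when censoring is at exit. Some bias remains if loss is informative.
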